14.2 NIH RAC Appendix B (excerpt)

Appendix B - Table 1. Basis for the Classification of Biohazardous Agents by Risk Group (RG)

Risk Group 1 (RG1)	Agents that are not associated with disease in healthy adult humans
Risk Group 2 (RG2)	Agents that are associated with human disease which is rarely serious and for which preventive or therapeutic interventions are often available
Risk Group 3 (RG3)	Agents that are associated with serious or lethal human disease for which preventive or therapeutic interventions may be available (high individual risk but low community risk)
Risk Group 4 (RG4)	Agents that are likely to cause serious or lethal human disease for which preventive or therapeutic interventions are not usually available (high individual risk and high community risk)

Appendix B-I. Risk Group 1 (RG1) Agents

RG1 agents are not associated with disease in healthy adult humans.

Appendix B-II. Risk Group 2 (RG2) Agents

RG2 agents are associated with human disease which is rarely serious and for which preventive or therapeutic interventions are *often* available.

Those agents not listed in Risk Groups (RGs) 3 and 4 are not automatically or implicitly classified in RG1 or 2; a risk assessment must be conducted based on the known and potential properties of the agents and their relationship to agents that are listed.

14.3 Criteria of Progression for Trial Eligibility by PCWG2 (2007)

Variable	PCWG2 (2007)
PSA	Obtain sequence of rising values at a minimum of 1-week intervals
	2.0 ng/mL minimum starting value
	Estimate pretherapy PSA-DT if 3 or more values available 4 or more weeks apart

14.4 ECOG Performance Status Criteria

These scales and criteria are used by doctors and researchers to assess how a patient's disease is progressing, assess how the disease affects the daily living abilities of the patient, and determine appropriate treatment and prognosis. They are included here for health care professionals to access.

ECOG PERFORMANCE STATUS*	
Grade	ECOG
0	Fully active, able to carry on all pre-disease performance without restriction
1	Restricted in physically strenuous activity but ambulatory and able to carry out work of a light or sedentary nature, e.g., light house work, office work
2	Ambulatory and capable of all selfcare but unable to carry out any work activities. Up and about more than 50% of waking hours
3	Capable of only limited selfcare, confined to bed or chair more than 50% of waking hours
4	Completely disabled. Cannot carry on any selfcare. Totally confined to bed or chair
5	Dead

* As published in Am. J. Clin. Oncol.:

The ECOG Performance Status is in the public domain therefore available for public use. To duplicate the scale, please cite the reference above and credit the Eastern Cooperative Oncology Group, Robert Comis M.D., Group Chair.

14.5 NYHA Classification – The Stages of Heart Failure

In order to determine the best course of therapy, physicians often assess the stage of heart failure according to the New York Heart Association (NYHA) functional classification system. This system relates symptoms to everyday activities and the patient's quality of life.

Class	Patient Symptoms
Class I (Mild)	No limitation of physical activity. Ordinary physical activity does not cause undue fatigue, palpitation, or dyspnea (shortness of breath).
Class II (Mild)	Slight limitation of physical activity. Comfortable at rest, but ordinary physical activity results in fatigue, palpitation, or dyspnea.
Class III (Moderate)	Marked limitation of physical activity. Comfortable at rest, but less than ordinary activity causes fatigue, palpitation, or dyspnea.
Class IV (Severe)	Unable to carry out any physical activity without discomfort. Symptoms of cardiac insufficiency at rest. If any physical activity

14.6 NCI Common Terminology Criteria for Adverse Events (NCI CTCAE v 4.0)

A copy of the CTCAE version 4.0 can be downloaded from the CTEP website at:
http://ctep.cancer.gov/protocolDevelopment/electronic_applications/ctc.htm.

A hard copy of the CTCAE version 4.0 can be found in the Study Instruction Manual.

14.7 FACT-P Quality of Life Questionnaire

FACT-P (Version 4)

Below is a list of statements that other people with your illness have said are important. Please circle or mark one number per line to indicate your response as it applies to the past 7 days.

PHYSICAL WELL-BEING		Not at all	A little bit	Some- what	Quite a bit	Very much
Q1	I have a lack of energy	0	1	2	3	4
Q2	I have nausea	0	1	2	3	4
Q3	Because of my physical condition, I have trouble meeting the needs of my family	0	1	2	3	4
Q4	I have pain	0	1	2	3	4
Q5	I am bothered by side effects of treatment	0	1	2	3	4
Q6	I feel ill	0	1	2	3	4
Q7	I am forced to spend time in bed	0	1	2	3	4

SOCIAL/FAMILY WELL-BEING		Not at all	A little bit	Some- what	Quite a bit	Very much
Q8	I feel close to my friends	0	1	2	3	4
Q9	I get emotional support from my family	0	1	2	3	4
Q10	I get support from my friends	0	1	2	3	4
Q11	My family has accepted my illness	0	1	2	3	4
Q12	I am satisfied with family communication about my illness	0	1	2	3	4
Q13	I feel close to my partner (or the person who is my main support)	0	1	2	3	4
Q14	Regardless of your current level of sexual activity, please answer the following question. If you prefer not to answer it, please mark this box  and go to the next section.					
Q15	I am satisfied with my sex life	0	1	2	3	4

FACT-P (Version 4)

Please circle or mark one number per line to indicate your response as it applies to the past 7 days.

EMOTIONAL WELL-BEING

		Not at all	A little bit	Some-what	Quite a bit	Very much
GE1	I feel sad	0	1	2	3	4
GE2	I am satisfied with how I am coping with my illness	0	1	2	3	4
GE3	I am losing hope in the fight against my illness	0	1	2	3	4
GE4	I feel nervous	0	1	2	3	4
GE5	I worry about dying	0	1	2	3	4
GE6	I worry that my condition will get worse	0	1	2	3	4

FUNCTIONAL WELL-BEING

		Not at all	A little bit	Some-what	Quite a bit	Very much
GF1	I am able to work (include work at home)	0	1	2	3	4
GF2	My work (include work at home) is fulfilling	0	1	2	3	4
GF3	I am able to enjoy life	0	1	2	3	4
GF4	I have accepted my illness	0	1	2	3	4
GF5	I am sleeping well	0	1	2	3	4
GF6	I am enjoying the things I usually do for fun	0	1	2	3	4
GF7	I am content with the quality of my life right now	0	1	2	3	4

FACT-P (Version 4)

Please circle or mark one number per line to indicate your response as it applies to the past 7 days.

ADDITIONAL CONCERNS		Not at all	A little bit	Somewhat	Quite a bit	Very much
21	I am losing weight.....	0	1	2	3	4
22	I have a good appetite	0	1	2	3	4
23	I have aches and pains that bother me.....	0	1	2	3	4
24	I have certain parts of my body where I experience pain...	0	1	2	3	4
25	My pain keeps me from doing things I want to do	0	1	2	3	4
26	I am satisfied with my present comfort level.....	0	1	2	3	4
27	I am able to feel like a man	0	1	2	3	4
28	I have trouble moving my bowels	0	1	2	3	4
29	I have difficulty urinating.....	0	1	2	3	4
30	I urinate more frequently than usual	0	1	2	3	4
31	My problems with urinating limit my activities.....	0	1	2	3	4
32	I am able to have and maintain an erection.....	0	1	2	3	4

7. What treatments or medications are you receiving for your pain?

8. In the last 24 hours, how much relief have pain treatments or medications provided? Please circle the one percentage that most shows how much relief you have received.

0%	10%	20%	30%	40%	50%	60%	70%	80%	90%	100%
No Relief										Complete Relief

9. Circle the one number that describes how, during the past 24 hours, pain has interfered with your:

A. General Activity

0	1	2	3	4	5	6	7	8	9	10
Does not Interfere										Completely Interferes

B. Mood

0	1	2	3	4	5	6	7	8	9	10
Does not Interfere										Completely Interferes

C. Walking Ability

0	1	2	3	4	5	6	7	8	9	10
Does not Interfere										Completely Interferes

D. Normal Work (includes both work outside the home and housework)

0	1	2	3	4	5	6	7	8	9	10
Does not Interfere										Completely Interferes

E. Relations with other people

0	1	2	3	4	5	6	7	8	9	10
Does not Interfere										Completely Interferes

F. Sleep

0	1	2	3	4	5	6	7	8	9	10
Does not Interfere										Completely Interferes

G. Enjoyment of life

0	1	2	3	4	5	6	7	8	9	10
Does not Interfere										Completely Interferes

Copyright 1991 [name]
Pain Research Group
All rights reserved.

14.9 EQ-5D-3L Quality of Life Questionnaire

By placing a checkmark in one box in each group below, please indicate which statements best describe your own health state today.

Mobility

- I have no problems in walking about
- I have some problems in walking about
- I am confined to bed

Self-Care

- I have no problems with self-care
- I have some problems washing or dressing myself
- I am unable to wash or dress myself

Usual Activities (e.g. work, study, housework, family or leisure activities)

- I have no problems with performing my usual activities
- I have some problems with performing my usual activities
- I am unable to perform my usual activities

Pain/Discomfort

- I have no pain or discomfort
- I have moderate pain or discomfort
- I have extreme pain or discomfort

Anxiety/Depression

[figure not shown]
- I am not anxious or depressed
- I am moderately anxious or depressed
- I am extremely anxious or depressed

US (English) © 1998 EuroQol Group. EQ-5D™ is a trade mark of the EuroQol Group

To help people say how good or bad a health state is, we have drawn a scale (rather like a thermometer) on which the best state you can imagine is marked 100 and the worst state you can imagine is marked 0.

We would like you to indicate on this scale how good or bad your own health is today, in your opinion. Please do this by drawing a line from the box below to whichever point on the scale indicates how good or bad your health state is today.

[figure not shown]
**Your own
health state
today**

14.10 Vial and Carton Labels

[figure not shown]
Labels are provided as reference only and are provided as examples. Specific label text and language may vary depending on country.

Labeling for Phase III PROSTVAC-V Outer carton label (Vaccinia)

[figure not shown]

Labeling for Phase III PROSTVAC-V and placebo vials:

Vial label: (All vial numbers shown are for demonstration purposes only)

[figure not shown]

Labeling for Phase III PROSTVAC-F Outer carton label (Fowlpox)

[figure not shown]

Labeling for Phase III PROSTVAC-F and placebo vials:

[figure not shown]
Vial label: (All vial numbers shown are for demonstration purposes only)

Labeling for Phase III GM-CSF Outer carton label

Bacteriostatic 0.9% Sodium Chloride for Injection, USP,
Secondary Package Label (for tray containing 25 vials, booklet label text)

14.11 List of Research Centers

A list of participating centers will be available on www.clinicaltrials.gov, or upon request to BNI. Actual centers may change over time. Additional sites may be identified and held in reserve in the event that some of the original sites discontinue participation, or if enrollment is slower than expected.

14.12 Rationale and Changes

14.12.1 Rationale

The main reason for this administrative amendment is to address feedback from the [REDACTED], who requested that the study protocol be updated to contain details regarding the Interim Analyses described in the Statistical Analysis Plan for this study. There is no impact to study design, conduct, or endpoints as a result of the language provided in Section 9.8, Interim Analyses.

In addition, the sponsor address and medical monitor have been updated.

14.12.2 Changes

General changes:

- Update Sponsor Address and Medical Monitor name
- Addition of Section 9.8, Interim Analyses and Section 14.12, Rationale and Changes
- Updated Abbreviation list

New text contained in the new Section 9.8, Interim Analyses is provided below

An interim analysis plan (IAP) is included in the SAP for this study. Interim analyses are executed by [REDACTED] a Contract Research Organization that acts as the independent statistician and assessed by the DMC as described in the DMC Charter. At each interim analysis, both unblinded (closed) and blinded (open) interim analysis reports will be provided to the DMC, while the sponsor will only receive an open (blinded) report unless one of the criteria is met. Even in this case, the DMC will use its discretion regarding the communications of results to the sponsor, with patient safety balanced against benefit being the primary concern.

The IAP was designed to detect early evidence of both efficacy and futility. Interim analyses for the two comparisons of overall survival described in Section 9.4 are to be executed at 40%, 60%, and 80% of information times, corresponding to 214, 321, and 427 deaths per comparison. The final analysis will be completed when 534 deaths per comparison have occurred. To maintain an overall one-sided type I error probability of 0.0125 per comparison, the one-sided significance criteria using one-sided O'Brien-

Flemming boundaries for early detection of efficacy analyses are 0.000135, 0.00147, 0.00501, respectively, with the adjusted final analysis to use 0.01063. The significance level to be used for detection of futility at each interim analysis is 0.00001. This futility significance level was chosen in order to provide a balance between the sought for estimated probability of detecting futility and protecting against falsely detecting futility.

9.1.2. Survival Status and Death.....	19
9.2. Clinical Laboratory Evaluations	19
9.3. Cardiac Markers.....	20
9.4. Vital Sign Measurements.....	20
9.5. Physical Examination.....	20
9.6. Electrocardiogram.....	20

9.7. Immune Monitoring.....	21
10. Quality of Life.....	21
11. Radiology.....	21
12. Interim Analysis.....	21
13. References.....	25
14. Appendix A: Delayed Effect Simulation Methodology.....	26
15. Appendix B: Linear Ramp and Accrual Rate	31
16. Appendix C: Imputation Algorithm for Partial and Missing Dates.....	32
17. Appendix D: List of Tables, Listings, and Figures.....	33

List of Abbreviations

ALP	Alkaline Phosphatase
ALT	Alanine Aminotransferase
AST	Aspartate Aminotransferase
ATC	Anatomical-Therapeutic-Chemical
AWE	Alive Without Event
BNI	Bavarian Nordic, Inc. Formerly known as BNIT
BPI-SF	Brief Pain Inventory – Short Form
BUN	Blood urea nitrogen
CK	Creatine Kinase
CK-MB	Creatine Kinase - Myocardial Band
CRP	C-Reactive Protein
CTC	Circulating Tumor Cell
CTCAE	Common Terminology Criteria for Adverse Events
CTMS	Clinical Trial Management System
DMC	Data Monitoring Committee
ECG	Electrocardiogram
eCRF	Electronic case report form
EOT	End-of-treatment
FACT-P	Functional Assessment of Cancer Therapy - Prostate
FAS	Full Analysis Set
GM-CSF	Granulocyte Macrophage Colony-Stimulating Factor
HBSAG	Hepatitis B Surface Antigen
HCT	Hematocrit
HCV	Hepatitis C Viral Load
HGB	Hemoglobin
IAP	Interim Analysis Plan
INR	International Normalized Ratio
ITT	Intent-to-Treat
LDH	Lactate dehydrogenase
LTFU	Long-term Follow-up

mCRPC	Metastatic castrate-resistant prostate cancer
MedDRA	Medical Dictionary for Regulatory Activities
NCI	National Cancer Institute
OS	Overall Survival
PAP	Prostatic Acid Phosphatase
PK	Pharmacokinetic
PPACT	Post-progression Anticancer Therapies
PSA	Prostate Specific Antigen
PT	Preferred Term
PTT	Partial Thromboplastin Time
QOL	Quality-of-life
RBC	Red Blood Cells
SAE	Serious Adverse Event
SC	Subcutaneous
SIP	Statistical Inference Plan
SOC	System Organ Class
TEAE	Treatment Emergent Adverse Event
WBC	White Blood Cells
WHO	World Health Organization

Revision History

SAP Version	SAP Date	Protocol Version	Reason for Change
Final	28 February 2013	Amendment 5	Initial version
Amendment 1	29 June 2015	Amendment 6	Updated per BNIT-PRV-301 protocol amendment 6

1. Introduction

PROSTVAC™ (PROSTVAC V and PROSTVAC F; PROSTVAC VF) is a novel candidate prostate cancer immunotherapy for the treatment of prostate cancer. It is a viral vector based product that is administered in seven subcutaneous vaccinations over a five month period. In a randomized controlled Phase 2 trial, PROSTVAC therapy was associated with a prolongation of survival in men with metastatic castration-resistant prostate cancer.

PROSTVAC is a PSA (prostate-specific antigen)-based immunization strategy. It is intended to generate immune responses to prostate specific antigens and prostate cancer cells. It uses poxviral vectors to introduce modified PSA to the subject in an immunogenic manner to break self-tolerance, and thereby induce immune responses directed against prostate cancer cells.

PROSTVAC is comprised of two component viral vectors; a recombinant vaccinia (PROSTVAC V) and a recombinant fowlpox (PROSTVAC F) virus to be used sequentially in a heterologous prime-boost vaccination regimen. Both viruses contain four human genes: prostate-specific antigen (PSA) and three genes encoding human immunological costimulatory molecules: B7.1, intercellular adhesion molecule-1 (ICAM-1), and leukocyte function-associated antigen-3 (LFA-3) (designated TR1ad of COstimulatory Molecules or TRICOM). The simultaneous expression of PSA and TRICOM enhances the immune response. The PSA transgene is modified at one amino acid (I155L), to enhance binding and immunogenicity of a particular peptide epitope in HLA-A2-expressing subjects.

2. Objectives

This is a randomized, double-blinded, placebo-controlled, multi-center, three-arm study. Subjects will be randomized with equal probability to one of three arms, designated as P, V, and VG for statistical purposes. A general description of the intended interventions to be applied to the subjects randomized to these three arms is: Placebo PROSTVAC + Placebo Granulocyte Macrophage Colony-Stimulating Factor (GM-CSF) for Arm P, PROSTVAC + Placebo GM-CSF for Arm V, and PROSTVAC + GM-CSF for Arm VG.

2.1. Primary Objective

The primary efficacy objective is to ascertain whether there is evidence for either Arm V or Arm VG to have superior survival outcome relative to Arm P.

2.2. Secondary Objective

To ascertain whether a greater proportion of subjects randomized to Arm VG or to Arm V remain event free at six months (or early termination) as compared to the subjects randomized to Arm P.

2.3. Exploratory Objectives

The Exploratory Objectives are:

- To evaluate whether HLA-A2 positive subjects have a larger survival effect size as compared to HLA-A2 negative subjects.
- To model the radiological disease status over the first year of study participation.
- To assess the role of post-treatment anti-cancer therapies as an alternative explanations for observed survival differences.
- To compare the arms with respect to immune responses to immunizing antigen (PSA), as well as to non-vaccine containing prostate antigens, and tumor-associated antigens, and to assess whether immune responses are prognostic.
- To compare the arms with respect to circulating tumor cell (CTC) levels.
- To model the role of arm, potential baseline prognostic factors, including baseline subject attributes and circulating tumor cells, immune responses, and the use of post-progression anti-cancer therapies as explanatory factors of survival.
- To model the relationship between tumor regression and growth rates and duration of survival.

3. Investigational Plan

3.1. Overall Study Design and Plan

BNIT-PRV-301 is a randomized, placebo-controlled, multi-center, Phase 3 efficacy trial of PROSTVAC in men with asymptomatic or minimally symptomatic, metastatic, castration-resistant prostate cancer. The study will consist of three periods: a Screening phase, followed by Treatment, and subsequently Long-term Follow-up (LTFU) phases.

Following the completion of the Treatment phase (after the last dose of PROSTVAC-V/F +GM-CSF or placebo or early termination of treatment) of the trial, all subjects will automatically enter the LTFU phase with study visits occurring every six months. During LTFU subjects will receive standard-of-care treatment as determined by the Principal Investigator. The appropriate timing and the nature of any subsequent treatment will be at the discretion of the Principal Investigator. All treatments for mCRPC subsequent to the Treatment phase of the trial will be documented in the electronic case report form (eCRF). This comprehensive data will be collected until study closure or death.

A detailed schedule of assessments can be found in the protocol.

3.2. Study Endpoints

3.2.1. Primary Endpoint

The primary endpoint is overall survival (OS). OS is defined as the time between the date of randomization and the date of death due to any cause. Subjects who do not experience death or the competing events of “definite” loss to follow-up or withdrawal of consent will be right censored at the date of last contact.

OS = Date of death/competing event/censoring - date of randomization+ 1.

3.2.2. Secondary Endpoint

The secondary efficacy endpoint for the study is the proportion of event-free subjects (AWE) (radiographic progression, pain progression, chemotherapy initiation, or death) at six months (or early termination) compared to placebo.

Progression events will be defined as:

- Radiographic progression (per central radiology assessment)
 - Two new lesions on bone scan, new metastases on CT scans*, or an increase size of nodal lesions per RECIST 1.1.
- Pain progression**
 - Introduction of scheduled opioid narcotics for cancer-related pain control. Scheduled opioid narcotics are defined as continuous daily use lasting more than 14 days.
- Initiation of chemotherapy for prostate cancer
- Death

* For subjects with allergies to contrast agents, MRIs for abdomen and pelvis may be performed. Only in cases where MRI is unavailable may a non-contrast CT be performed.

** The start date for an event of pain progression is defined as day 1 of first opioid regimen lasting more than 14 days.

Radiographic progression will be assessed by bone scan or CT at Screening, Week 13, Week 25 (EOT), and early termination scans. For secondary endpoint analysis, Screening scans and Week 13, Week 25 (EOT), and early termination scans will be compared by central radiology review. Bone scan and CT data will be archived up to five years past the end of the trial.

The secondary efficacy endpoint is a binary assessment for AWE at six months. Subjects without an event prior to six months will have an evaluation for event at six months. Subjects without event who are not evaluated at six months will be assumed to have had an event. Thus, each subject will be defined as AWE = 1 if the subject is alive and free of event at six months and AWE = 0 otherwise. AWE will have a realization for every subject and therefore is amendable to an intent-to-treat analysis.

The analysis of AWE is less subject to ascertainment anomalies compared to the analysis of time-to-progression because the six month assessment brings all subjects to the same level of ascertainment.

3.2.3. Exploratory Endpoint

The exploratory efficacy endpoint for the study is the proportion of subjects Alive Without Event (AWE) (radiographic progression, pain progression, chemotherapy initiation, or death) at the 6 month LTFU visit compared to placebo. For all subjects alive at the Week 25 (EOT) visit we will assess AWE at the 6 month LTFU visit. Subjects with pain progression or initiating

chemotherapy for prostate cancer at the Week 25 (EOT) visit will be counted as having an event at the 6 month LTFU visit.

Progression events at the 6 month LTFU visit will be defined as:

- Radiographic progression (per central radiology assessment) taking the Week 25 (EOT) visit scan as baseline
 - Two new lesions on bone scan, new metastases on CT scans*, or an increase size of nodal lesions per RECIST 1.1.
- Pain progression**
 - Introduction of scheduled opioid narcotics for cancer-related pain control. Scheduled opioid narcotics are defined as continuous daily use lasting more than 14 days.
- Initiation of chemotherapy for prostate cancer
- Death

* For subjects with allergies to contrast agents, MRIs for abdomen and pelvis may be performed. Only in cases where MRI is unavailable may a non-contrast CT be performed.

** The start date for an event of pain progression is defined as day 1 of first opioid regimen lasting more than 14 days.

This will attempt to define effects on secondary progression, and characterize delayed effects of investigational vaccine therapy.

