To ascertain whether the overall survival of subjects randomized to Arm V+G (PROSTVAC-V/F plus GM-CSF) or to Arm V (PROSTVAC-V/F) is superior to that from subjects randomized to Arm P (placebo control).

Secondary Efficacy Objective:

To ascertain whether a greater proportion of subjects randomized to Arm V+G or Arm V remain event-free (radiological progression, pain progression, chemotherapy initiation, or death) at 6 months (or early termination) as compared to the subjects randomized to Arm P.

Safety Objectives:

To further characterize the safety and tolerability of PROSTVAC immunotherapy.

Exploratory Objectives:

To model radiological disease status over the first year of study participation.

To ascertain whether a greater proportion of subjects randomized to either Arm V+G or Arm V remain event-free (radiological progression) 6 months post End-of-Treatment visit (using scans at End-of-Treatment visit as a new baseline) as compared to the subjects randomized to Arm P. This analysis will include all subjects, and the HLA-A2-expressing subgroup.

To assess the role of post-treatment anti-cancer therapies as an alternative explanation for observed survival differences.

To ascertain whether the overall survival of HLA-A2-expressing subjects randomized to Arm V+G, or Arm V is superior to that from HLA-A2-expressing-subjects randomized to Arm P.

To compare arms with respect to immune response to immunizing antigen (PSA), as well as to non-vaccine-contained prostate antigens, and tumor-associated antigens, and assess whether immune responses are prognostic and/or predictive.

To evaluate for baseline biomarkers which are prognostic and/or predictive of long-term survival outcome.

To compare arms with respect to vaccine effects on circulating tumor cell (CTC) levels (US sites).

Study Type

Pivotal

Methodology

- Subcutaneous immunizations
 - PROSTVAC-V or placebo administered in Week 1
 - PROSTVAC-F or placebo administered in Weeks 3, 5, 9, 13, 17, and 21.

Trial Population

Subjects with asymptomatic or minimally symptomatic, metastatic prostate cancer who have progressed despite surgical castration or androgen suppression therapy. Subjects will have evidence of radiological disease progression, or PSA disease progression as described in Prostate Cancer Clinical Trials Working Group 2 (PCWG2) criteria, after being treated with androgen suppression therapy or complete androgen blockade and withdrawal.

Sample Size

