3.1.2.1 Definition of Event (To be Used in Secondary Endpoint)

Progression events will be defined as:

- Radiographic progression
 - Two new lesions on bone scan, new metastases on CT scans*, or an increase size of nodal lesions per RECIST 1.1.
- Pain progression
 - Introduction of scheduled opioid narcotics for cancer-related pain control.
- Initiation of chemotherapy
- Death

* For subjects with allergies to contrast agents, MRIs for abdomen and pelvis may be performed. Only in cases where MRI is unavailable may a non-contrast CT be performed. For subjects enrolled in Germany, MRI must be used as the primary imaging modality.

Radiographic progression will be assessed by bone scan at 3 and 6 months, and by CT scan (or MRI for subjects in Germany) at 6 months (and at the time of progression, or any time during the treatment period if clinically indicated). For secondary endpoint analysis, baseline scans and 6 month scans (or early termination scans) will be compared by central radiology review. Bone scan and CT (or MRI for subjects in Germany) data will be archived up to five years past the end of the trial.

In addition, for an exploratory endpoint, we will assess radiological progression at 12 months (6 months post End-of-Treatment visit) by comparison with the 6 month scans (from End-of-Treatment visit or early termination). This will attempt to define effects on secondary progression, and characterize delayed effects of investigational vaccine therapy.

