3.1.4 Exploratory Objectives

To model secondary radiological disease progression over the first year of study participation.

To ascertain whether a greater proportion of subjects randomized to either Arm V+G or Arm V remain event-free (radiological progression) six months post End-of-Treatment visit (using scans at End-of-Treatment visit as a new baseline), as compared to the subjects randomized to Arm P. This analysis will include all subjects, and separately the HLA-A2-expressing subgroup.

To assess the role of post-treatment anti-cancer therapies as an alternative explanation for observed survival differences.

To ascertain whether the survival of HLA-A2-expressing subjects randomized to Arm V+G, or Arm V is superior to that from HLA-A2-expressing-subjects randomized to Arm P.

To ascertain whether a greater proportion of HLA-A2 expressing subjects randomized to Arm V+G or to Arm V remain event-free at six months as compared to the HLA-A2 expressing subjects randomized to Arm P.

To compare arms with respect to immune response to immunizing antigen (PSA), as well as to non-vaccine containing prostate antigens, and tumor-associated antigens, and assess whether immune responses are prognostic and/or predictive.

To evaluate for baseline biomarkers which are prognostic and/or predictive of long term survival outcome.

To compare arms with respect to vaccine effects on circulating tumor cell (CTC) levels (US sites only).

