8.5.2. Absence of Progression at 12 Months

To model the likelihood of remaining radiologically event-free at 12 months as compared to scans at 6 months is of interest. Subjects may become secondarily stable, allowing for time for the vaccine to induce an immune response, and then establish a new baseline at 6 months. The between-arm comparison of this outcome is not a comparison free of the confounding of post-randomization events that have the potential of being arm-dependent. Regression modeling of being free of progression, which is AWE at 12 months, with covariates for baseline prognostic factors and AWE at 6 months, will be conducted.

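### The protocol's delayed-effect endpoint (radiological progression from an End-of-Treatment baseline, overall and in HLA-A2-expressing men) is replaced in the SAP by a composite that mixes in early pain and chemotherapy events, and the change is not declared

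*SAP*

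**What the plan says.** **Protocol.** The synopsis and section 3.1.4 state the objective as whether more men in either vaccine arm "remain event-free (radiological progression) six months post End-of-Treatment visit (using scans at End-of-Treatment visit as a new baseline"). Both add that the analysis covers all subjects and the HLA-A2-expressing subgroup. Section 3.1.2.1 repeats the definition: "we will assess radiological progression at 12 months (6 months post End-of-Treatment visit) by comparison with the 6 month scans". It gives the purpose as well: "This will attempt to define effects on secondary progression, and characterize delayed effects of investigational vaccine therapy".

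**SAP 3.2.3** keeps that purpose sentence but changes the endpoint: "The exploratory efficacy endpoint for the study is the proportion of subjects Alive Without Event (AWE) (radiographic progression, pain progression, chemotherapy initiation, or death"), assessed at the 6-month long-term follow-up (LTFU) visit. The radiographic component is reset, "taking the Week 25 (EOT) visit scan as baseline". The other two non-fatal components are not. Men with pain progression, or starting "chemotherapy for prostate cancer at the Week 25 (EOT) visit will be counted as having an event at the 6 month LTFU visit".

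**SAP 8.4** analyses this composite by stratified logistic regression in the ITT set, leaving out men not alive at Week 25. It specifies no subgroup.

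**SAP 8.5.2** says that remaining radiologically event-free from the 6-month to the 12-month scans is of interest, then specifies "Regression modeling of being free of progression, which is AWE at 12 months", with AWE at 6 months among the covariates.

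**SAP 4.4** names two changes from the protocol: tumor regression and growth rates, and interim analysis.

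**The concern.** The same purpose is attached to two different outcomes. The protocol asks whether, once the vaccine has had time to act, scans stay stable from a fresh starting point. The SAP asks whether a man is free of four kinds of event, two of which may already have been present at that starting point.

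Two things are at stake. First, the protocol's stated objective would have no estimate, either overall or in HLA-A2-expressing men. Second, a result on the SAP's endpoint could not be read as a delayed effect. A difference could come from events during the treatment phase, and a real late difference could be masked by them.

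**Working it through.** **Step 1. How each definition treats events before the new baseline**

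| Event up to Week 25/EOT | Protocol 3.1.2.1, 3.1.4 | SAP 3.2.3, 8.4 |
|---|---|---|
| Radiographic progression | Reset at EOT scan | Reset at EOT scan |
| Death | Not named as an event | Subject excluded |
| Pain progression | Not part of endpoint | Counted as event at LTFU visit |
| Chemotherapy started | Not part of endpoint | Counted as event at LTFU visit |

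The SAP thus handles pre-baseline events in three ways: reset, exclude and carry forward. The result is neither a new-baseline endpoint nor AWE counted from randomization.

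**Step 2. Does any other part of the SAP estimate the protocol's endpoint?**

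- SAP 2.3 keeps a general aim to model radiological status over the first year, but not the new-baseline comparison of proportions.
- SAP 8.5.2 names the radiological question, but the outcome it models is AWE.
- SAP 8.5.1 examines HLA-A2 for survival only. The general effect-modifier analyses in 8.2.4 and 8.3.2 concern survival and six-month AWE.
- SAP 11 only lists radiology data.
- The contents of Appendix D (tables, listings and figures) are not in the text available, so this step rests on the body of the SAP.

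The SAP was updated to protocol Amendment 6. By its own change list (14.12.2), Amendment 7 adds the interim-analysis text and administrative updates, so it does not explain the difference.

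**Step 3. Which way could the carry-forward push the result?**

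Neither document gives an expected rate, effect size or significance level for this endpoint. The nearest figures are for six-month AWE in SAP 8.3: 400 per arm, control 0.50, one-sided 0.0125, critical difference 0.080, and at least 90% power at a difference of 0.126. They reproduce:

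- Critical difference: 2.2414 × √(2 × 0.25/400) = 0.079.
- Power at 0.50 versus 0.626, pooled-variance normal formula: 91.3%.

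(Protocol 9.6 gives 0.1375 and 0.092 for the same quantities, which do not reproduce at 0.0125. That is a separate matter.) I borrow 0.50 and 0.626 only as an example of a late difference.

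Let q be the control share of men carried forward, and r the vaccine-to-control ratio of that share. Among the rest, let 0.50 and 0.626 be event-free. Then:

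observed difference = (1 − rq) × 0.626 − (1 − q) × 0.50 = 0.126 − q × (0.626r − 0.50)

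Both q and r are assumptions.

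| q | r = 1 | r = 0.90 | r = 0.75 |
|---|---|---|---|
| 0.05 | 0.120 | 0.123 | 0.128 |
| 0.10 | 0.113 | 0.120 | 0.129 |
| 0.20 | 0.101 | 0.113 | 0.132 |
| 0.30 | 0.088 | 0.107 | 0.135 |
| 0.40 | 0.076 | 0.101 | 0.138 |

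Break-even is r = 0.50/0.626 = 0.80, whatever q is. Above it the late difference shrinks; below it the difference grows.

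Now suppose there is no late effect, with 0.50 event-free in both arms among the rest. The difference is 0.50 × q × (1 − r). With q = 0.30 and r = 0.75 it is 0.50 × 0.30 × 0.25 = 0.0375, produced wholly by early events.

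**The case against.** The strongest reply has three parts.

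- **The endpoint is exploratory.** It has no alpha or power target, SAP 8.5.2 already warns that this outcome is confounded by post-randomization events, and nothing confirmatory depends on it. This stands, and it limits the weight of the point. It does not supply the missing analysis.
- **The carry-forward has a rationale.** A man already on chemotherapy may have stable scans because of it, and counting him as a failure avoids crediting that to the vaccine. This is a fair reason to keep the composite as a supportive view. It does not justify dropping the protocol's outcome without saying so.
- **The harm might be overstated.** A reader might infer that the carried-forward events are the same in both arms, so that they necessarily dilute a delayed effect and cost a calculable amount of power. The documents do not support that. The delay in SAP 4.1.3 (hazard ratio 1 for four months, then a ramp to 0.68 by month 8) is a planning assumption for survival and is not applied to opioid or chemotherapy starts. The secondary objective tests for fewer events in the same composite by six months. If the vaccine lowers early pain or chemotherapy events enough, carry-forward inflates the difference.

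It would also be too broad to say that all earlier failures are carried forward. Only pain progression and chemotherapy are. SAP 3.2.3 ties the rule to the Week 25 visit, and reading that as any start up to Week 25 is an inference for the sponsor to confirm.

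**Conclusion.** The mismatch is established from the text alone. The protocol's radiology-only endpoint from the EOT baseline has no matching analysis in the body of the SAP, its HLA-A2 version is not planned, SAP 8.5.2 equates two different outcomes, and SAP 4.4 is silent on the change.

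The effect on the estimate cannot be sized from the documents, and its direction is unknown. With the borrowed 0.126 difference and an assumed 5% to 40% of controls carried forward, the observed difference runs from 0.120 down to 0.076 if early rates are equal, and from 0.128 up to 0.138 if the vaccine rate is three quarters of control. These figures show the mechanism only and do not predict a loss of power.

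Primary and secondary inference are unaffected. This should be corrected so that the trial can answer its own exploratory objective, but it is not critical.

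**What to change.** - In SAP 8.4, add as the named exploratory endpoint centrally reviewed radiographic progression from the Week 25/EOT scan to the 6-month LTFU scan, overall and in HLA-A2-expressing subjects. Do not carry forward Week 25 pain progression or chemotherapy.
- If death after the EOT scan is to count as an event, declare it as an addition to the protocol's definition.
- Keep men with pain progression or chemotherapy at Week 25 in the main analysis, judged on their scans. Show results without them only as a sensitivity view, because leaving them out conditions on a post-randomization event.
- Keep the four-part composite as supportive, and state whether its rule means at, or at any time up to, Week 25.
- Correct SAP 8.5.2 so that it does not equate radiological stability with AWE, and list the change in SAP 4.4.

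The cost is SAP wording and one more table. The scans are already scheduled at EOT and at the first LTFU visit, and SAP 3.2.3 already provides for central review. The drawback is that chemotherapy started before Week 25 may delay radiographic progression in some men, which is why the composite and the sensitivity view should stay alongside.
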